9.3.3. Secondary Analyses

Following secondary efficacy variables will be analysed for both completers (those who completed entire 9 months of study) and ITT population.

The secondary efficacy variables are:

- Frequency of GI and respiratory illnesses defined as total number of illness episodes of GI and/or respiratory illnesses, divided by duration of intervention, where each episode is defined as each incidence of illness followed by at least 3 symptom free days (Section 6.11.2).

The same model outlined above for primary outcome variable will be used for this secondary outcome.

- Severity of GI and respiratory illnesses (Mild, moderate, or severe intensity as captured in DF) (See Section 6.11.2 for details on capturing severity of illness).

This will be captured by study physician as per severity grading outlined in Appendix 5. Frequencies of intensity (Mild, moderate, or severe) by treatment groups will be compared using chi-square test (if frequencies are greater than 5%). If frequencies are $\leq 5\%$ in any treatment groups, then these will be compared using Fisher's exact test between treatment groups.

- School absenteeism due to GI and respiratory illnesses as identified from DF.

The same model outlined above for primary outcome variable will be used for this secondary outcome.

- Change from baseline (measured at screening visit) in BMI.

This will be analysed using an analysis of covariance (ANCOVA) model. The model will include the fixed factors for treatment, cluster (school) and gender; baseline BMI assessment recorded at screening visit as covariate.

- Change from baseline in gut integrity/health as measured by Lactulose:Mannitol test and Urinary Neopterin test defined in Section 6.9.1.1 respectively.

 GlaxoSmithKline	Document Name	Clinical Study Protocol 204477		
	Type	Version	Document Identifier	Effective Date
	eldo_clinical_doc	5.0; Most-Recent; Effective; CURRENT	090032d580daa95e	10-Oct-2017 06:16:49
	Reason For Issue	Auto Issue		

These will be analysed using an ANCOVA model. The model will include the fixed factors for treatment, cluster (school) and gender; baseline gut integrity/health assessment at baseline as covariate.

- Change from baseline in salivary IgA as defined in Section 6.9.1.2.

This will be analysed using an ANCOVA model. The model will include the fixed factors for treatment, cluster (school), and gender; baseline salivary IgA assessment at baseline as covariate.

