STATISTICAL REPORTING AND ANALYSIS PLAN

CLINICAL STUDY TO MEASURE THE IMPACT OF FORTIFIED MALT BASED FOOD ON IMMUNITY OUTCOMES IN SCHOOL CHILDREN

Protocol Number: 204477

Phase: N/A

Property of GSK Consumer Healthcare
Confidential
May not be used, divulged, published or otherwise disclosed
without the consent of GSK

Template Version Effective: 15-Jul-2017

Document History

| Document | Version Date | Summary of Changes (New analysis or Change in planned analysis) |
|------------------------|-----------------|--|
| Original Analysis Plan | 27-June -2018 | Not applicable (N/A) |
| Amendment 1 | 2-November-2018 | 
 1. For all ANCOVA analyses, “cluster (school)” will be included as a random effect instead of a fixed effect. Handling “cluster” as random effect would avoid over-parametrisation and would allow for intracluster correlation. 2. Present the estimate of the intra cluster correlation in the ANCOVA tables. Adjusting for the intracluster correlation is necessary for a valid analysis. 3. Implementation of comments received during dry-run process. 4. Creation of additional corresponding descriptive statistics tables for exploratory ANCOVA tables. 5. Removal of raw outputs in section 16.1.9 with no corresponding ANCOVA tables in section 14.2. 6. Replacing originally planned figures with corresponding tables. |

Table of contents

| | |
|---|----|
| Document History | 2 |
| Table of contents | 3 |
| Abbreviations | 5 |
| 1 Summary of Key Protocol Information | 7 |
| 1.1 Study Design..... | 7 |
| 1.2 Study Objectives | 9 |
| 1.3 Treatments | 11 |
| 1.4 Sample Size Calculation | 11 |
| 2 Planned Analyses..... | 12 |
| 2.1 Interim Analysis..... | 12 |
| 2.2 Final Analyses | 12 |
| 3 Considerations for data analyses and Data Handling Conventions..... | 13 |
| 3.1 Baseline Definition | 13 |
| 3.2 Subgroups/Stratifications..... | 13 |
| 3.3 Centers Pools | 13 |
| 3.4 Time points and Visit Windows | 13 |
| 4 Data Analysis..... | 13 |
| 4.1 Populations for Analysis..... | 14 |
| 4.1.1 Subject Disposition | 14 |
| 4.1.2 Protocol Deviations | 14 |
| 4.1.3 Analysis Populations | 15 |
| 4.2 Subject Demographics and Other Baseline Characteristics..... | 16 |
| 4.2.1 Demographic Characteristics | 16 |
| 4.2.2 General Medical History | 17 |
| 4.2.3 Characteristics of Disease | 17 |
| 4.3 Treatments (Study Product, Rescue Medication, other Concomitant Therapies, Compliance)..... | 17 |

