1.4 Sample Size Calculation

The primary efficacy variable of the study is the total number of ill days due to GI and respiratory illnesses. The sample size has been calculated based on the assumption of an average of 7 ill days in the control group with a difference of 10% between the treatments.

Years Lost due to Disability (YLD) is a measure of the burden of disease from its morbidity. Below are data that are specific to India: As per the data from Global Burden Disease, WHO 2010 study (GBD, WHO, 2012; IHME, 2013) and Census India, 2011, YLD per child in the 5-9-year age group, due to diarrhea, LRTIs, other infectious disease and nutritional deficiencies is 8.274 days/child per year or 6.21 days/child per 9 months.

Thus, based on above data, approximately 7 ill days due to GI and respiratory illnesses per 9 months has been assumed in this proposed study population of 7-10 year olds.

The sample size is based on the primary endpoint. No sample size considerations have been taken into account for secondary objectives.

The simulated data were also used based upon the assumption of a Poisson distribution per study treatment. On observation of these simulated data, it was considered that these Poisson distributions were not heavily skewed and, as a result, normal distributions may be

assumed. Consequently, a normality assumption has been adopted for both the generation of sample size and the intended approach to the statistical analysis.

Because of assumption of Poisson distribution, estimates of variability were calculated as square root of mean.

Mean of control was assumed to be 7.0 and standard deviation (SD) was 2.65, mean of test group was 6.3 and SD was 2.51. To be able to achieve 80% power, 215 participants per treatment arm (Total = 430) will be required to complete the study in case of individual randomisation. This assumes 5% level of significance (two tailed t-test).

As this study is using cluster randomization, and design effect (DE) needs to be considered for sample size calculations. Scientific literature suggests, DE due to cluster sampling strategy can be assumed to be 1.5 [Rosner, B, 1986]. Same has been assumed in one study, which used three-stage systematic cluster sampling [Dandona R *et al*, 2008].

Using the following formula from Hemming *et al*, 2011:

$$N^* = N \times DE$$

Where N^* = Number of participants required for cluster randomized trial

N = Number of participants required for individual randomization

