4.4.1.2 Statistical Hypothesis, Model, and Method of Analysis

For the primary variable, primary analysis will be performed on participants on the mITT population.

The null hypothesis of interest is:

H0: There is no difference between the numbers of illness days for the product groups.

The alternative hypothesis of interest is:

H1: There is a difference in between the numbers of illness days for the product groups.

The number of ill days will be analysed using the analysis of variance (ANCOVA) model. The ANCOVA will have cluster (school) as a random effect, product group and gender as fixed effects and baseline IDDS as a covariate.

Adjusted means, 95% confidence intervals (CI), within product group p-values for each product group, product group difference, intracluster correlation, 95% confidence interval of the difference and the between-product group p-values based on the statistical model described above will also be presented ([Table 14.2.2.2](#)).

All statistical tests of hypotheses will be two-sided and will employ a level of significance of $\alpha = 0.05$.

The simulated data used for the sample size calculations were based upon the assumption of a Poisson distribution per product group. However, on observation of these simulated data, it was considered that these Poisson distributions were not heavily skewed and, as a result, normal distributions may be assumed. Consequently, a normality assumption has been adopted for both the generation of sample size and the intended approach to the statistical analysis.

However, the assumptions of normality and homogeneity of variance will be investigated and violation of these assumptions may be overcome using suitable transformation (for example, log or square root or Poisson regression using Proc Genmod) or by performing appropriate non-parametric tests (e.g., Van Elteren, rank ANCOVA).

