4.4.2 Secondary Efficacy Variables

The analysis of secondary efficacy variables will be on the mITT population.

The secondary efficacy variables are:

- **Frequency of GI and Respiratory illness**

Frequency of GI and respiratory illnesses defined as total number of illness episodes of GI and/or respiratory illnesses, divided by duration of intervention in month, where each episode is defined as each incidence of illness followed by at least 3 symptom free days will be summarized in a table for the product groups (Table 14.2.3.1).

The frequency of GI and respiratory illnesses will be calculated as following –

Frequency (per month) = No of episodes X 30/ Number of days between first (BV) and last visit

Frequency of GI and respiratory illnesses will be analysed together using analysis of covariance (ANCOVA) model. The model will include cluster (school) as a random effect; fixed effects for product group and gender; and baseline IDDS as a covariate. Adjusted means, 95% confidence intervals, intraclass correlation, within product group p-values for each product group, product group difference, 95% confidence interval of the difference and the between-product group p-values based on the statistical model described above will also be presented (Table 14.2.3.2).

The assumptions of normality and homogeneity of variance will be investigated and violation of these assumptions may be overcome using suitable transformation or by performing sensitivity analysis or by appropriate non-parametric tests (e.g., Van Elteren, rank ANCOVA).

- **Analysis on Severity of GI and Respiratory illness:**

Frequency and percentages of severity episodes of GI and respiratory illnesses will be summarized in a table together and also separately (Table 14.2.4.1). If an episode comprises of occurrences of different severities, then the highest severity will be considered as the overall severity. Severity grades will be displayed in the tables for the GI and respiratory illness as mentioned in the Appendix 5 of the Protocol version 5.0.

Frequencies of severity (Mild, moderate, or severe) episode between product groups will be compared using Chi-Square test (if frequencies are greater than 5%). If frequencies are $\leq 5\%$ in any product group, then these will be compared using Fisher's exact test between product groups (Table 14.2.4.1).

- **Analysis of School absenteeism due to GI and Respiratory illness:**

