4.6 Exploratory Analysis

- **Analysis of number of ill days over 3 and 6 months:**

The number of ill days due to GI and respiratory illnesses over 3 months and 6 months separately on the ITT population who have completed the study for 3 months and 6

GlaxoSmithKline Consumer Healthcare Confidential

months will be summarized and analyzed using the same model as used in the primary analysis (Table 14.2.13.1.1 and Table 14.2.13.1.2).

- **Analysis of total number of ill days for GI and respiratory illness separately over 3, 6 and 9 months:**

Primary analysis and the above analysis will be repeated for total number of ill days for GI and respiratory illness separately at months 3, 6 and 9 based on the ITT population (Table 14.2.13.2.1 and Table 14.2.13.2.2 for GI illness) and (Table 14.2.13.3.1 and Table 14.2.13.3.2 for respiratory illness).

- **Analysis of total number of ill days due to GI and respiratory illnesses, school absenteeism (days), frequency (per month), severity by gender at 9 months:**

It will be summarized and analysed and presented as detailed for the primary and secondary endpoint respectively by gender (Table 14.2.13.4.1 and Table 14.2.13.4.2 for ill days due to GI and respiratory illnesses), (Table 14.2.13.7.1 and Table 14.2.13.7.2 for school absenteeism (days)), (Table 14.2.13.5.1 and Table 14.2.13.5.2 for frequency (month)) and severity of episodes (Table 14.2.13.6.1).

- **Analysis of change from baseline of HAZ, Height and Weight:**

Change from baseline in HAZ, height and weight will be summarised and analysed using the same ANCOVA model as mentioned for the BMI analysis (Table 14.2.13.8.1 and Table 14.2.13.8.2 for HAZ), (Table 14.2.13.9.1 and Table 14.2.13.9.2 for height), (Table 14.2.13.10.1 and Table 14.2.13.10.2 for weight).

- **Association between Gut integrity/health as measured by Lactulose: Mannitol test and Urinary Neopterin test with blood chemistry:**

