| 
 9.3.2 9.3.3 | 
 For all ANCOVA analyses, "cluster (school)" will be included as a random | 
 Handling "cluster" as random effect would avoid over-parametrisation and would allow for intracluster correlation. |

| Protocol | Reporting & Analysis Plan | |
|---|--|---|
| Statistical Analysis section | Statistical Analysis Plan | Rationale for Changes |
| 
 9.3.5 | 
 effect instead of a fixed effect. Present the estimate of the intra cluster correlation in the ANCOVA tables. | 
 Adjusting for the intracluster correlation is necessary for a valid analysis. |

6 Template for Tables, Figures and Listings

This is a guideline which will give the guidance of product group labels that will be used for the table header and in the figures, listings and in the footnotes.

The product group labels for the column headings will be as follow:

Test Group and Control Group;

The product group comparison will be:

- Test Group vs Control Group

The order of the product groups will be following-

- 1st: Test Group
- 2nd: Control Group

In all the outputs following footnote will be added –

Test Group: Fortified malt based food + Dietary Counselling

Control Group: Dietary Counselling

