| MODERATE | xx (xx.x) | xx (xx.x) | | |
| SEVERE | xx (xx.x) | xx (xx.x) | | |

Fortified malt based food

204477 Statistical Reporting and Analysis Plan Amendment 1 2 November 2018

| PREFERRED TERM SEVERITY | Test Group (N=XXX) | Control Group (N=XXX) | P-VALUE[1] | P-VALUE[2] |
|----------------------------|--------------------|--------------------------|------------|------------|
| RESPIRATORY ILLNESS | | | | |
| MILD | xx (xx.x) | xx (xx.x) | 0.xxx | 0.xxx |
| MODERATE | xx (xx.x) | xx (xx.x) | | |
| SEVERE | xx (xx.x) | xx (xx.x) | | |

Test Group: Fortified malt based food + Dietary Counselling; Control Group: Dietary Counselling

[1] p-value is from the Chi-Square test.

[2] p-value is from the Fisher's exact test.

The numbers are based on the episodes with worst severity.

Program: xxxxxx.sas

Source: Filename

Page x of y

Programming note: The table will represent on the episodes

Fortified malt based food

204477 Statistical Reporting and Analysis Plan Amendment 1 2 November 2018

Protocol 204477

Program Run Date: DDMMYYYY

Table 14.2.6.1
Summary of BMI (kg/m2)
Modified Intent-to-Treat Population

Study Population: Modified Intent-to-Treat Population (N = xxx)

| Visit | Statistics | Test Group (N = xxx) | | Control Group (N = xxx) | | Overall (N = xxx) | |
|-----------|------------|-------------------------|----------------------|----------------------------|----------------------|----------------------|----------------------|
| | | Observed Value | Change from Baseline | Observed Value | Change from Baseline | Observed Value | Change from Baseline |
| SCREENING | n | xxx | | xxx | | xxx | |
| | MEAN | xx.xx | | xx.xx | | xx.xx | |
| | SD | xx.xxx | | xx.xxx | | xx.xxx | |
| | SE | x.xx | | x.xx | | x.xx | |
| | MEDIAN | x.xx | | x.xx | | x.xx | |
| | MINIMUM | xx.x | | xx.x | | xx.x | |
| | MAXIMUM | xx.x | | xx.x | | xx.x | |
| MONTH 9 | n | xxx | xxx | xxx | | xxx | |
| | MEAN | xx.xx | xx.xx | xx.xx | | xx.xx | |
| | SD | xx.xxx | xx.xxx | xx.xxx | | xx.xxx | |
| | SE | x.xx | x.xx | x.xx | | x.xx | |

Fortified malt based food

204477 Statistical Reporting and Analysis Plan Amendment 1 2 November 2018

Protocol 204477

Program Run Date: DDMMYYYY

Table 14.2.6.2
 Statistical Analysis of BMI (kg/m²) Change from Baseline at Month 9
 Modified Intent-to-Treat Population

Study Population: Modified Intent-to-Treat Population (N = xxx)

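### Severity of illness is tested by chi-square or Fisher on episodes, with no allowance for repeated episodes in a child or for school, although schools are the randomised units

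*SAP*

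**What the plan says.** **Severity.** SAP 4.4.2: "Frequencies of severity (Mild, moderate, or severe) episode between product groups will be compared using Chi-Square test (if frequencies are greater than 5"%); when frequencies are 5% or less in either group, Fisher's exact test replaces it. An episode containing occurrences of different severity takes the highest grade. The shell for Table 14.2.4.1 notes: "The numbers are based on the episodes with worst severity". It has columns for both p-values and none for an intracluster correlation, unlike the ANCOVA shells. SAP 4.6 repeats the analysis by gender: "severity of episodes (Table 14.2.13.6.1").

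Protocol 9.3.3 plans the same choice of test: "Frequencies of intensity (Mild, moderate, or severe) by treatment groups will be compared using chi-square test". It does not say whether the unit is the child, the occurrence or the episode.

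**Design.** Protocol 5.9.1 randomises schools within matched pairs. SAP 3.3 gives four schools, two per group.

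**Amendment 1.** The SAP's Document History and section 5 state that, for the ANCOVA analyses, school "will be included as a random effect instead of a fixed effect", and that the intracluster correlation will be tabulated. The reason given is: "Adjusting for the intracluster correlation is necessary for a valid analysis".

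**Related text.** SAP 4.4.2 also compares IDDS categories by chi-square or Fisher, without school. If model assumptions fail for the primary endpoint, SAP 4.4.1.2 permits a log or square-root transformation, or "Poisson regression using Proc Genmod) or by performing appropriate non-parametric tests (e.g., Van Elteren, rank ANCOVA"). Van Elteren is named again for each secondary endpoint analysed by ANCOVA. None of these sentences says how school is handled.

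**The concern.** A chi-square or Fisher test on pooled episodes assumes that every episode is independent of every other. Here that can fail at two levels. A child who tends to have severe illness contributes several similar episodes. Children in one school also share exposures, a local study physician and reporting habits. Each school is wholly in one arm, so differences between schools go straight into the treatment comparison.

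The SAP has accepted this argument for its ANCOVA analyses. Severity is not an ANCOVA, so the correction did not reach it. What is at stake is a secondary p-value that could support a claim of milder illness when part of the apparent evidence is child-to-child or school-to-school variation.

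**Working it through.** **1. The plan's own clustering figure.** SAP 1.4: "Scientific literature suggests, DE due to cluster sampling strategy can be assumed to be 1.5". This is applied to ill days: 215 × 1.5 = 322.5, rounded up to 323 per arm, 646 in total. That reproduces the plan.

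**2. Implied school correlation for ill days.** Children per school: 646 / 4 = 161.5. ICC = (DE − 1)/(m − 1) = 0.5/160.5 = 0.0031.

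**3. What carries over to severity.** The documents give no DE, ICC, category split or episode count for severity. Nor are DE 1.5 and ICC 0.0031 the same assumption once episodes are counted:
- 2 episodes per child: 323 episodes per school, DE = 1 + 322 × 0.0031 = 2.0.
- 4 episodes per child: 646 episodes per school, DE = 1 + 645 × 0.0031 = 3.0.

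The calculation below therefore uses one basis throughout, an ICC on a latent severity scale.

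**4. Simulated rejection rate of the three-category chi-square test under no effect.** Assumptions: four schools of about 161 children, two per arm; 2 or 4 episodes per child; mild/moderate/severe split 60/30/10; nominal level 5%.

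| Latent child correlation | Latent school ICC | Rejection rate |
|---|---|---|
| 0 | 0 | about 5% |
| 0.1 to 0.5 | 0 | about 5.5% to 16% |
| 0 | 0.0031 | about 11% to 17% |
| 0.3 | 0.0031 | about 13% to 21% |

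The lower end of each range is 2 episodes per child and the upper end is 4; in the second row the child correlation also runs from 0.1 to 0.5. A repeat run agreed to within about a point, except that the last upper end came out near 23%. Letting the number of episodes vary between children (Poisson with mean 2 or 4) gave 7% to 17% for child correlation 0.2 to 0.4 alone, and 12% to 27% with school ICC 0.0031 added. The Fisher branch was not simulated.

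**5. Fallbacks for the primary, if run without school.** DE 1.5 does apply to ill days. For a 1-df test that ignores clustering:

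2 × P(Z > 1.96/√1.5) = 2 × P(Z > 1.60) = 0.110.

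Simulation with Poisson counts of mean 7 gave about 10.5% for Poisson regression, Van Elteren and rank ANCOVA alike. Van Elteren cannot be stratified by school, because a one-arm stratum contains no comparison. Stratifying by matched pair is possible but leaves school-to-school variation unadjusted.

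**The case against.** - **The test need not be badly wrong.** With negligible child and school correlation the chi-square test is close to 5%. A reader might infer that the severity p-value is invalid whatever the data show. The documents do not support that. They show a test with no protection against clustering, and its error depends on correlations they do not report.
- **The protocol does not fix the episode as unit.** Protocol 9.3.3 supports only the choice of test. The episode unit comes from SAP 4.4.2 and the shell, and the criticism of repeated episodes is directed there.
- **DE 1.5 is not a severity figure.** Applying it directly would give 9.2% to 13.6% for a three-category table. It belongs to ill days at about 161 children per school, so those rates should not be read as what the plan implies for episodes.
- **The fallback wording is permissive.** It speaks of suitable or appropriate methods and gives the non-parametric tests as examples. Section 5 calls adjustment necessary, so a statistician following it could include school, and the random-school requirement may already cover rank ANCOVA. A reader might infer that the plan commits to an unadjusted primary test; it does not. Data with variance equal to the mean are also what the SAP regards as close enough to normal, so 11% is not the error rate given that a fallback is triggered.
- **The consequence is limited.** Protocol 9.2.3 defines success on ill days alone. Frequency, absenteeism and IDDS change have random-school models, and ill days also has a random-school MMRM and summaries by school.

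These points set the size and scope. They do not alter the severity text: followed exactly, it produces a test without child or school in a trial that randomises four schools.

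**Conclusion.** The severity analysis is wrong as written and should be fixed. Under positive child or school correlation its p-value is too small, and it does not meet the standard the SAP sets for itself. The same applies, for school only, to the IDDS-category test, which matters less because IDDS change already has a random-school ANCOVA.

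The direction is clear; the size is not documented. The rates in the table, from about 5.5% to 21% against a nominal 5%, rest on assumed episode counts, severity split and latent correlations, and cover only the chi-square branch.

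The fallback wording is a secondary clarification. It matters only if a fallback is triggered and then run without school; the plan's own DE would then give about 11%. Log and square-root transformations keep the random school effect and are not at issue.

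**What to change.** 1. In SAP 4.4.2 and 4.6, present severity (overall and by gender) and IDDS categories as counts and percentages without chi-square or Fisher p-values. Remove the p-value columns from Tables 14.2.4.1, 14.2.11.3 and 14.2.13.6.1 as applicable. Severity can remain episode-based.
2. If a severity test is wanted, name one school-level proportion in advance, for example the share of episodes that are moderate or severe, and compare it on between-school degrees of freedom, stating whether the matched pairs are used.
3. Record the change in SAP section 5, because protocol 9.3.3 plans the tests being removed.
4. In SAP 4.4.1.2 and the secondary paragraphs of 4.4.2, add one sentence: any Poisson, Van Elteren or rank fallback must account for school, and the method must be stated.

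The cost is SAP wording and table-shell edits, and the loss of a secondary p-value. If the school-level test is kept, four schools leave few degrees of freedom and little power; that follows from the design and is not caused by this change. No new data are needed.

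### Severity is tested only as the mix of grades among episodes that occurred, so no planned analysis tests whether moderate or severe illness per child fell

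*SAP*

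**What the plan says.** Protocol section 2 and SAP 1.2 list severity of GI and respiratory illness among the secondary objectives, to be compared between participants in the two groups over nine months. Protocol 6.11.2 (item C) defines the outcome at episode level, as the intensity of an illness episode.

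The planned test is the same in both documents. Protocol 9.3.3: "Frequencies of intensity (Mild, moderate, or severe) by treatment groups will be compared using chi-square test". SAP 4.4.2: "Frequencies of severity (Mild, moderate, or severe) episode between product groups will be compared using Chi-Square test". If a frequency is 5% or less in either group, "then these will be compared using Fisher's exact test between product groups".

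The SAP fixes the unit: "If an episode comprises of occurrences of different severities, then the highest severity will be considered as the overall severity". In Attachment 1, the footnote to the Table 14.2.4.1 shell reads "The numbers are based on the episodes with worst severity", and its programming note reads "The table will represent on the episodes". The shell has rows for mild, moderate and severe within each illness block, and no row for children without an episode. SAP 4.6 repeats the severity analysis by gender (Table 14.2.13.6.1). Neither document plans a per-child rate by grade or a worst grade per child.

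**The concern.** Whether an episode occurs is itself something the product is meant to change. A comparison restricted to episodes that occurred therefore compares groups selected after treatment started, and children who stayed well drop out of it. The test sees only the shares of the three grades. Shares can move when one grade falls and the others stay put, and they stay put when all grades fall together.

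At stake is how the severity objective is read. A product that reduced moderate and severe illness in proportion to everything else would get a null severity result. One that prevented only mild illness would show a mix tilted towards the worse grades. In neither case does the p-value say whether children had less moderate or severe illness.

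**Working it through.** **Inputs.** The documents give no figure for severity: no episode rate, no grade mix and no power calculation (SAP 1.4 excludes secondary objectives from sample size). The only planned figures used here are the 323 evaluable children per arm (215 × 1.5 = 322.5, rounded up) and the 10% difference planned for ill days. Everything else is assumed. The first illustration takes 1000 control episodes split 65/30/5% into mild, moderate and severe. At 323 children that is 1000/323 = 3.1 episodes per child.

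**Method.** Pearson chi-square on the 2 × 3 table of episodes by arm and grade, 2 degrees of freedom, applied to the expected counts. Each expected cell is row total × column total / grand total. Fisher's test would use the same six counts, so the argument carries over to it.

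**1. The product prevents 30% of mild episodes and nothing else.**
- Control 650/300/50 (total 1000); test 455/300/50 (total 805).
- Episodes fall by 195/1000 = 19.5%.
- Moderate-or-severe share: 350/1000 = 35.0% against 350/805 = 43.5%.
- Expected cells: control 612.19/332.41/55.40; test 492.81/267.59/44.60.
- Chi-square = 2.335 + 3.160 + 0.527 + 2.901 + 3.925 + 0.654 = 13.50; p = 0.0012.
- Moderate-or-severe episodes per child: 350/323 = 1.08 in both arms, so no difference.
- With 500 control episodes p = 0.034; with 323 (one per child) p = 0.11.

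**2. Same, with a 10% effect.**
- Test 585/300/50 (total 935). Share: 350/935 = 37.4% against 35.0%.
- Chi-square = 1.24; p = 0.54.

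**3. The product prevents 30% of every grade.**
- Test 455/210/35 (total 700). The shares are 65/30/5% in both arms, chi-square on the expected counts is 0, and the test rejects only at about its nominal 5%.
- Moderate-or-severe episodes per child fall from 350/323 = 1.08 to 245/323 = 0.76, a rate ratio of 0.70.
- This result does not depend on the assumed rate, mix or sample size.

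**4. Sensitivity to the assumptions.** With 323 children per arm, 2 control episodes per child and a 60/30/10% mix:
- 30% mild-only effect: the share moves from 40.0% to 48.8%, chi-square 9.11, p = 0.0105. Over 1 to 3 episodes per child, and with either this mix or 80/17/3%, p runs from 0.21 to 0.001.
- 10% mild-only effect: 40.0% to 42.6%, p = 0.66.
- 30% fall in every grade: moderate-or-severe episodes are 258.4 against 180.9. A per-child rate test gives z = (180.9 − 258.4)/√(258.4 + 180.9) = −3.70, p = 0.0002. In simulation its power is about 96%, against a rejection rate of about 5% for the planned test.

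All these p-values and powers treat episodes as independent. Repeat episodes in one child and clustering by school would weaken them.

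**The case against.** The strongest reply is that Protocol 6.11.2 defines the outcome as the severity of an episode and lists it separately from ill days, frequency and absenteeism. On that definition, if every grade falls by 30%, episodes are fewer but no milder, and a null result is the right answer to the question as defined. This stands. A reader might infer that the planned test has the wrong denominator; the documents do not support that. It is a valid description of a narrow quantity, severity given an episode. What the reply does not meet is that SAP 1.2 frames the objective as a comparison of participants, and a contrast among episodes selected after treatment does not provide one.

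Second, benefit could show elsewhere. Ill days, episode frequency and school absenteeism are analysed over all mITT children, including those never ill, and Appendix 5 of the protocol partly grades moderate illness by its effect on school attendance. Table 14.2.4.1 also prints the episode counts by grade, so 50 against 35 severe episodes would be visible. This stands too: a general fall in illness need not go unnoticed. But frequency pools all grades, and none of these analyses tests moderate or severe illness per child.

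Third, a reader might infer that the plan would make a helpful product look harmful, or give the opposite of the true answer. That goes too far. A 2 × 3 chi-square or Fisher test has no direction, and the counts next to the shares would show moderate and severe episodes unchanged. The risk is misreading the shares.

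**Conclusion.** The point holds in limited form. The planned severity test answers whether the grade mix of episodes differs between groups. It does not answer whether children given the product had less moderate or severe illness, and no other planned analysis does.

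The insensitivity to an equal fall in all grades is exact and needs no assumption. The shift under a mild-only effect is real in direction but uncertain in size: it rests on an assumed mix, episode count and effect, and at the 10% planned for ill days it is small and far from significance. The 30% cases are illustrations and not forecasts.

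Severity is a secondary endpoint, and by Protocol 9.2.3 study success rests on ill days alone, so the primary conclusion is untouched. The change is still worth making, because the severity objective is otherwise left without a randomised comparison.

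**What to change.** In SAP 4.4.2, add for every mITT child the rate of moderate-or-severe episodes over follow-up, set to zero if there were none. Analyse it with the episode-frequency model: school as a random effect, product group and gender as fixed effects, baseline IDDS as covariate. If counts are sparse, use a count model such as the Poisson regression already named in SAP 4.4.1.2, keeping the allowance for school. This also brings in the adjustment for intracluster correlation, which SAP section 5 calls necessary and the chi-square omits.

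Apply the same measure to the by-gender severity analysis (Table 14.2.13.6.1). Keep Table 14.2.4.1 as a description of episode grade, and state that its chi-square and Fisher p-values are not to be read as a treatment effect on children. Record the change in SAP section 5.

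The cost is one extra table and a documented departure from Protocol 9.3.3. No new data are needed: the Diagnosis Form already records grade and dates for each occurrence.
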